9.3 Archiving

It is the responsibility of the Principal Investigator to ensure that all essential trial documentation and source records (e.g. signed Informed Consent Forms, ISFs, pharmacy files, patients' hospital notes) at their site are securely retained for at least 10 years after the end of the trial. Data held by CTR will be stored in a secure archive facility. Following authorisation from the sponsor, arrangements for confidential destruction will then be made.

9.4 Confidentiality and data protection

Personal data recorded on all documents will be regarded as strictly confidential and will be handled and stored in accordance with the Data Protection Act (1998). With the patient's consent, their full name, date of birth, National Health Service (NHS) number (or in Scotland the Community Health Index [CHI]), hospital number and general practitioner details will be collected at trial entry to allow tracing through the NHS Information Centre for Health and Social Care (service formerly provided by the Office for National Statistics) to assist with follow-up. Patients will be identified using only their unique trial number, initials, hospital number and date of birth on the CRF and in any correspondence between CTR and the participating site. Patients are asked, however, to give permission for CTR to be sent a copy of their signed Informed Consent Form which will not be anonymised. This will be used to perform in-house monitoring of the consent process. Where copies of source documents are required by CTR for central monitoring purposes, the patient's name must be obliterated by the site before sending.

The Investigator must maintain documents not for submission to CTR in strict confidence. In the case of specific issues and/or queries from the regulatory authorities, it will be necessary to have access to the complete trial records, provided that patient confidentiality is protected.

CTR will maintain the confidentiality of all patient data and will not disclose information by which patients may be identified to any third party other than those directly involved in the treatment of the patient and organisation for which the patient has given explicit consent for data transfer (e.g. Cancer Registries, laboratory staff). Representatives of the Monocle trial team may be required to have access to patients' notes for quality assurance purposes but patients should be reassured that their confidentiality will be respected at all times. If a patient withdraws consent from further trial treatment and/or further collection of data their information will remain on file. All collected data will be included in the final study analysis.

10 STATISTICAL CONSIDERATIONS

10.1 Sample size and early stopping rules

Up to 40 patients will be recruited to the study, all of whom will receive tefinostat therapy. The proposed trial design (Bryant and Day)¹⁶⁾ is based on Simon's two-stage design, but incorporates toxicity as well as clinical efficacy (futility) considerations into sample size and early stopping rules.

The primary clinical efficacy objective of the study is to determine overall response rate after 6 cycles of tefinostat. It is felt that if the overall response rate is below 10% the treatment should be rejected, and if above 30% the treatment is sufficiently promising to warrant further evaluation in a phase III trial. These figures reflect the minimum clinically relevant response rate seen in the CMML-201 study of azacitidine therapy in a similar CMML patient population. (17)

The primary safety and tolerability objective is to determine the proportion of patients who suffer an unacceptable level of toxicity as assessed during the first 2 cycles of tefinostat treatment. It is felt that if more than 40% of patients suffer unacceptable toxicity then the treatment should be rejected, and if fewer than 20% suffer some toxicity then the toxicity profile is considered acceptable. A maximum tolerated dose is often defined as the dose at or below the level at which one-third of patients experience toxicity and these figures correspond to that definition.

The significance level for both the efficacy and tolerability endpoints was chosen to be 10%. This is the bound of probability of recommending a treatment with either inadequate efficacy or unacceptable safety. The two-stage design was chosen to allow for early termination in the event of unacceptable toxicity or lack of efficacy. Under these conditions, and setting power at 85% for both the efficacy and safety endpoints, a maximum of 40 evaluable patients need to be recruited into the study. The first stage will recruit up to 19 patients and will require 6 or fewer to have unacceptable toxicity, with at least 3 patients showing clinical benefit (as defined in section 8.3) in order to proceed to the second stage.

Tefinostat will be considered for further randomised clinical evaluation if at least 7 of 40 patients respond according to the specified clinical response criteria, and fewer than 13 patients exhibit unacceptable toxicity (ie. at least 28patients are able to tolerate the drug. Those patients who are not known to have responded will be deemed non-responders. All patients who receive at least one dose of study drug will be considered evaluable, and as such non-compliance is expected to be minimal. There are no plans to replace patients that

withdraw from the study. Experience from the CMML201 study shows that compliance with follow-up is likely to be very good in this disease population. (17)

10.2 Data analysis

Statistical analysis will be overseen by [name], Professor of Translational Statistics at Cardiff University and CTR Lead. Analysis will be descriptive for the defined primary and secondary endpoints of the trial (proportions of patients with response/toxicity). The analysis population (patients evaluable for the primary endpoints) will include any patient starting one cycle of tefinostat therapy.

10.3 Independent Data Monitoring Committee (IDMC) and formal interim analysis

An Independent Data Monitoring Committee (IDMC) will review the accumulating safety and efficacy results of the trial on a continuous basis and a formal interim analysis will be performed after a sufficient number of evaluable patients have been treated to be able to determine whether the continuation criteria for progression to the second stage of the study have been met (see section 10.1). Recruitment to the study may thus need to be temporarily halted after the first 19 patients to allow sufficient safety and clinical efficacy data to accumulate. The IDMC will also have the power to request to suspend recruitment or stop the study at any time in the setting of emerging safety concerns. CTR will send safety and efficacy data, along with current recruitment figures to the IDMC whenever they are notified of a new treatment-related death or grade 3/4 non-haematological adverse reaction. To inform the decision of whether or not to proceed to the second stage of the study, overall response rates following completion of cycle 3 of tefinostat may be presented to the IDMC as an early indication of response. All analyses will be kept confidential until the end of the study.

10.4 Definition of outcome measures

10.4.1 Primary outcome measures

- Safety and tolerability of tefinostat will be defined as the proportion of patients experiencing a CTC grade 3-4 non-haematological toxicity⁽²⁵⁾ or death during the first two cycles of tefinostatthat is judged by either the principal investigator or the chief investigator (or his delegate) as having a reasonable suspected causal relationship to tefinostat.
- Overall clinical response rate will be defined as the cumulative proportion of patients achieving clinical benefit (or better) according to International Consortium MDS/MPN Response Criteria⁽²⁸⁾ at day 29 of the sixth or last cycle of tefinostat (whichever is the earliest).

10.4.2 Secondary outcome measures

- Incidence of CR / PR / clinical benefit will be defined according to the International Consortium MDS/MPN Response Criteria⁽²⁸⁾ (see Appendix 3) at day 29 of the sixth or last cycle of tefinostat (whichever is the earlier). Duration of response will be measured from the date of investigations confirming the achievement of response until the date on which it is confirmed that the patient is no longer sustaining response.
- Overall clinical response rate according to Wattel and Modified IWG criteria (see Appendix 4 and 5).
 Responses will be defined as the cumulative proportion of patients achieving minor response of better (according to Wattel criteria⁽¹⁴⁾ and/or haematological improvement or better (according to the Modified IWG criteria)⁽²³⁾ at day 29 of the sixth or last cycle of tefinostat (whichever is the earliest).
- Red blood cell transfusion independence will be deemed to have been achieved if a patient who
 received red cell transfusion support in the eight weeks prior to baseline assessment remains free
 from red cell transfusion for a period of ≥ eight weeks
- Platelet transfusion independence will be deemed to have been achieved if a patient who received
 platelet transfusion support in the eight weeks prior to baseline assessment remains free from
 platelet transfusion for a period of ≥ eight weeks
- Overall survival is defined as the time from the date of trial registration to the date of death from any
 cause. Patients discontinuing the study, lost to follow-up or still alive at the end of study will be
 censored at the date of last follow-up.
- Progression-free survival is defined as the time from date of trial registration to the date of progression
 or death from CMML. Patients who die from a cause other than CMML prior to progression will be
 censored in the analysis. The date of progression is the date of the decision to investigate a clinical
 suspicion of progression which is subsequently confirmed.
- Time to AML transformation of CMML is defined as the time from trial registration to AML transformation of CMML or last follow-up. Patients in whom CMML does not transform to AML will be censored at the last date they were known to be alive and free from AML transformation of CMML. The date of AML transformation of CMML is the date of the decision to investigate clinical suspicion of AML transformation which is subsequently confirmed.
- Duration of tefinostat therapy is defined as the time elapsed between first and last doses of tefinostat therapy.
- Quality of life will be measured using the MPN-SAF and EuroQoL EQ-5D-5L questionnaires

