7.5 Patients with uncontrolled myeloproliferation

For patients who have uncontrolled myeloproliferation, the concomitant use of hydroxycarbamide is permitted. Patients who are already receiving hydroxycarbamide therapy at the time of trial entry will be allowed to continue hydroxycarbamide at the time of initiation of tefinostat treatment. The introduction of hydroxycarbamide is also permitted, at the discretion of local investigators, for WBC persistently $\geq 30 \times 10^9 / l$. Investigators should make every effort, according to individual patient circumstances, to wean and stop hydroxycarbamide as patients continue on tefinostat therapy. The concomitant use of hydroxycarbamide will not be permitted following completion of the third cycle of tefinostat (week 12) and patients with uncontrolled myeloproliferation beyond this time point will be withdrawn from the study.

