7.6.1 Dose reductions for toxicities related to tefinostat

Toxicities will be graded using the NCI CTCAE version 4 (Appendix 8).

No modification in tefinostat dose is required for grade 1-2 toxicities.

In the event of grade 3 or 4 toxicity considered possibly, probably or definitely related to tefinostat, the study drug should be temporarily discontinued and the next treatment cycle delayed until the toxicity has resolved to grade 1 or less. Thereafter, the drug should be recommenced at a dose reduced by one dose level (120mg/day); patients previously taking 360mg should be reduced to 240mg, patients taking 240mg should be reduced to 120mg. The lowest permitted tefinostat dose is 120mg daily. Attempts to re-escalate the tefinostat dose following resolution of toxicity will be at the discretion of the investigator, but should not be made until the patient has completed a full 28-day cycle at the reduced dose without additional grade 3-4 toxicity; if the same AE occurs a second time further dose escalations will not be permitted.

If a grade 3 or 4 toxicity considered related to tefinostat does not resolve to grade 1 or less within 28 days, the patient will be removed from the study but should continue to undergo follow-up evaluations (please refer to section 8.5 for patient evaluations required in these circumstances).

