8.5 Assessment at disease progression or cessation of therapy due to unacceptable toxicity

For patients who stop tefinostat treatment at *time points other than immediately following the post cycle 6 efficacy response* assessment the following additional assessments should be performed. This will include patients in whom tefinostat is

withdrawn early (during cycles 1-5) due to unacceptable toxicity or clear disease progression (including those patients with uncontrolled myelosuppression who require concomitant hydroxycarbamide therapy beyond completion of tefinostat cycle 3 – see section 7.5) and also patients who stop tefinostat treatment due to disease progression or toxicity following a prolonged period of therapy extending beyond cycle 6.

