8.6 Early withdrawal from the trial

Participants have the right to withdraw their consent from the study at any time for any reason. Should a patient decide to withdraw from the study, all efforts should be made to report the reason for withdrawal as thoroughly as possible. The investigator should ascertain from which aspects of the trial the patient wishes to withdraw and record the details in the appropriate part of the CRF (Form F). If a patient chooses to withdraw from treatment only the patient should continue to be assessed in accordance with the protocol. If a patient wishes to withdraw from the trial (i.e. including trial-specific assessments)

but is willing for further data to be supplied to CTR, then further routine follow-up data such as disease response status, survival and further treatment, will continue to be supplied by the investigator to CTR until 18 months after registration.

The local investigator also has the right to withdraw patients from the study treatment for a number of justifiable reasons including unacceptable toxicity (an adverse event or events that, in the judgment of the investigator, may cause severe or permanent harm or which rule out continuation of the study drug), unforeseen events which in the opinion of the investigator make further treatment inadvisable, serious violation of the study protocol (including persistent patient non-attendance and non-compliance) or for clinical reasons not related to the study treatment. Patients withdrawn by the investigator should continue to undergo safety assessments as per the trial schedule and to receive supportive care as per local policy.

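### Overall survival in section 10.4.2 censors patients who discontinue the study even where their death is recorded, and sections 7.5 and 7.6.1 blur who those patients are

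*Protocol*

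**What the plan says.** **The endpoint.** Protocol 10.4.2: "Overall survival is defined as the time from the date of trial registration to the date of death from any" cause. The censoring sentence follows: "Patients discontinuing the study, lost to follow-up or still alive at the end of study will be" "censored at the date of last follow-up".

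**Who leaves the study.** Section 7.5, on hydroxycarbamide after the third cycle (week 12): "patients with uncontrolled myeloproliferation beyond this time point will be withdrawn from the study". Section 7.6.1, on related grade 3 or 4 toxicity that does not resolve within 28 days: "the patient will be removed from the study but should continue to undergo follow-up evaluations".

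**What is still collected.**
- Sections 4.3 and 10.5 require at least 18 months of follow-up from registration, expressly to assess OS and progression-free survival.
- Section 8.6, for patients who leave trial procedures but allow data to be supplied: "further routine follow-up data such as disease response status, survival and further treatment, will continue to be supplied" until 18 months after registration.
- Section 9.1 schedules 12-month and 18-month forms from trial entry, with no exception for patients who have stopped.
- Section 9.4 takes identifiers, with consent, "to allow tracing through the NHS Information Centre for Health and Social Care". Speaking of patients who withdraw consent, it adds that all data already collected enter the final analysis.
- Section 11.6 has every death recorded on a death report form.

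**The concern.** The censoring sentence names three alternative groups. Being alive qualifies only the third, so a patient who discontinues the study is censored whether or not a death is later recorded. That conflicts with an all-cause death endpoint and with a follow-up scheme built to capture those deaths.

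The rule can reach identifiable patients. Someone recorded as withdrawn from the study at week 12 for uncontrolled myeloproliferation who dies at month 6 could be analysed as censored, with the death form on file. Patients removed for uncontrolled disease plausibly have a worse outlook than those who stay, so such censoring would be informative. At stake is whether the reported survival curve describes all treated patients or mainly those who remained on study.

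**Working it through.** **1. Text check.** The OS sentence does not limit censoring to patients not known to have died, and it does not define discontinuing the study. The time-to-AML rule in the same section censors patients without transformation at the last date known alive and AML-free, so the protocol already has the safer form for a neighbouring endpoint.

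**2. Direction and possible size.** The protocol states no OS target, event count or power, so there is no figure to reproduce. An illustrative model was used instead.

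Inputs from the protocol:
- Background median survival of 11-17 months (section 2.1), used only to set a plausible scale; medians of 11, 14 and 17 were tried.
- Removal at about week 12 (section 7.5), taken as month 3.
- Evaluation at 18 months (sections 4.3 and 10.5).
- Up to 40 patients (section 10.1).

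Assumptions, which the documents do not give:
- Exponential survival with hazard λ for patients who stay.
- A share *q* (10-40%) of those alive at month 3 is removed.
- The death hazard after removal is HR × λ, with HR from 1 to 3.

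True survival for *t* > 3 is

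S(t) = e^(−3λ) × [(1−q) e^(−λ(t−3)) + q e^(−HR·λ(t−3))],

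with λ solved so that S equals 0.5 at the chosen median. Two literal readings are compared with it:
- **A**, censored at removal: Kaplan-Meier recovers the stayers' curve, S_A(18) = e^(−18λ).
- **B**, censored at last follow-up, taken as the death date, with the death not counted. After month 3 the apparent hazard is λ times the stayers' share of those at risk.

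*Worked case: median 14 months, q = 20%, HR = 2.* This gives λ = 0.0438.
- True: 0.877 × (0.8 × 0.518 + 0.2 × 0.269) = 0.411.
- A: e^(−18 × 0.0438) = 0.454; apparent median ln 2 / 0.0438 = 15.8 months.
- B: exp{−0.1315 − ln[(e^0.657 + 0.25)/1.25]} = exp{−0.688} = 0.50; apparent median about 18 months.

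In a trial of 40, about 40 × 0.877 × 0.2 = 7 patients are removed. About 7 × (1 − 0.269) = 5 of them die by month 18, out of 40 × (1 − 0.411) ≈ 24 deaths in all. Those 5 are the deaths at risk of going uncounted.

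| Median 14, HR = 2 | True 18-month OS | A | B |
|---|---|---|---|
| q = 10% | 41% | 43% | 46% |
| q = 20% | 41% | 45% | 50% |
| q = 30% | 41% | 48% | 55% |
| q = 40% | 41% | 50% | 60% |

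Across medians of 11-17 months, q of 10-40% and HR of 1.5-3, 18-month OS is overstated by about 1-14 percentage points under A and 4-22 under B. With HR = 1, A has no bias, while B still overstates by about 3-15 points because deaths become censored times.

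**3. After the fix.** Counting every known death returns the true curve: 18-month OS of about 32%, 41% and 48% for medians of 11, 14 and 17 months.

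**The case against.** The strongest defence is that discontinuing the study simply means leaving follow-up, so only patients with no recorded death are censored. Several passages support this. The event is death from any cause, and censoring ordinarily applies to those without the event. Section 7.6.1 itself keeps removed patients under follow-up. Section 8.5, cross-referring to 7.5, describes those patients as having tefinostat "withdrawn early (during cycles 1-5) due to unacceptable toxicity or clear disease progression (including those patients with" uncontrolled blood counts needing hydroxycarbamide, which is end of treatment. Section 8.6 separates stopping treatment from leaving the trial. The three sections also use different verbs (discontinuing, withdrawn, removed); only the words for the study are shared. This stands as a possible reading and lowers the certainty. It does not remove the defect, because 10.4.2 does not say it and the term is undefined.

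A reader might infer that toxicity removals under 7.6.1 also carry a worse prognosis. That is less certain: unresolved toxicity does not by itself establish higher mortality, and under A with equal hazards there is no bias.

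The precision argument also has weight. With 40 patients the standard error of an 18-month OS of 41% is about √(0.41 × 0.59/40) = 8 points, so shifts at the low end of the range sit within sampling noise. A systematic upward shift is nevertheless not excused by a wide interval.

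Finally, censoring detail is often left to an analysis plan. Here the protocol fixes the rule itself, so an analysis plan that follows it would inherit the problem.

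**Conclusion.** The point holds as a defect of wording with a real possible consequence. Taken literally, 10.4.2 censors patients whose deaths the protocol collects. Upward bias follows under either of two conditions: the date of death is used as a censoring date, or patients are censored at removal and removed patients have higher mortality (plausible for uncontrolled disease, less certain for toxicity). The range of about 1 to 22 points at 18 months rests on assumed removal shares, hazards and a single removal time; the documents cannot narrow it.

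Two stronger conclusions that a reader might draw are not supported. One is that survival will certainly be overstated: the lenient reading remains open. The other is that a distorted figure would be judged against the 11-17 month median in section 2.1. No such comparison is planned, and that median runs from diagnosis, whereas OS here runs from registration and includes previously treated patients.

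OS is secondary and its analysis descriptive (section 10.2). The stage 1 and final decision rules in 10.1 use response and toxicity only and are unaffected. The change should be made, but it does not threaten the design.

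**What to change.** In 10.4.2, delete discontinuing the study as a reason for censoring OS. State that every death known by data cut-off counts, whether or not the patient has stopped tefinostat or left trial procedures. Censor only patients not known to have died, at the date last known alive, drawing on the follow-up forms, the data supplied under 8.6, the death report forms and the tracing in 9.4. Censor at withdrawal only where the patient refuses further data.

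Reconcile the wording of 7.5 and 7.6.1 with 8.5 and 8.6 so that end of study treatment is distinguished from end of follow-up. This is terminology only and changes no clinical rule.

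The cost is a few sentences and no new data. The reported survival figure may be slightly less favourable.

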1 TRIAL FLOW DIAGRAM

2 BACKGROUND

2.1 Chronic Myelomonocytic Leukaemia (CMML)

Chronic myelomonocytic leukaemia (CMML) is a myelodysplastic / myeloproliferative neoplasm with a high median age of presentation (75 years) and a poor prognosis; the median survival from diagnosis remains only 11-17 months. The incidence of CMML is poorly defined, although large population-based studies estimate that CMML constitutes approximately 10% of cases of myelodysplastic syndrome (MDS) where the overall incidence of MDS is approximately 4 cases per 100,000 per year and rises to a level of >30 / 100,000 / year beyond the age of 70. Due to its relative rarity, its clinical and morphological heterogeneity and its overlap with other myeloid neoplasms, CMML has been a historically under-researched disease entity, with few clinical studies addressing it in isolation.

CMML has a highly heterogeneous disease phenotype with individual patients showing varying degrees of 'dysplastic' and 'proliferative' disease features. It is characterised by peripheral blood monocytosis (>1x10⁹/l), bone marrow failure and accompanying blood cytopenias, sometimes in association with leucocytosis and other myeloproliferative features such as hepatosplenomegaly, constitutional symptoms and infiltration of the skin and other organs. In 1982, CMML was included as one of five MDS categories within the French-American-British (FAB) classification on the basis of marrow dysplasia, clonal cytogenetic abnormalities and a propensity for progression to acute myeloid leukaemia (AML).⁽⁴⁾ Since 2001, the WHO classification has moved CMML into a separate category of 'mixed myelodysplastic / myeloproliferative neoplasms' where the disease has been additionally sub-divided into CMML-1 (with <10% bone marrow blasts) and CMML-2 (with 10-19% blasts) based on the powerful prognostic weighting of the bone marrow blast count. ⁽⁵⁾ A rare separate entity, the category of 'CMML with eosinophilia' has also been created; this is associated with translocations involving 5q33 (platelet-derived growth factor receptor) and a high degree of therapeutic sensitivity to imatinib mesylate therapy; CMML with eosinophilia is not representative of the bulk of CMML cases and falls outside the scope of the Monocle study.

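### The endpoint labelled progression-free survival censors deaths not attributed to CMML, including tefinostat-related deaths, so it overstates PFS whenever such deaths precede progression

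*Protocol*

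**What the plan says.** Section 10.4.2 opens the definition with "Progression-free survival is defined as the time from date of trial registration to the date of progression" and completes the event with death from CMML only. The next sentence deals with the remaining deaths: "Patients who die from a cause other than CMML prior to progression will be" "censored in the analysis". It makes no exception for treatment-related death.

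The bullet directly above uses a different rule for overall survival: "Overall survival is defined as the time from the date of trial registration to the date of death from any" cause.

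The protocol foresees deaths caused by the drug. In Section 10.4.1 the primary safety endpoint includes death in the first two cycles judged as "having a reasonable suspected causal relationship to tefinostat". In Section 10.3 the IDMC receives data whenever the trials unit is "notified of a new treatment-related death or grade 3/4 non-haematological adverse reaction".

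Section 11.6 collects the date and cause of every death. The synopsis and Sections 3.2.2, 4.3 and 10.5 name PFS without defining it. Appendices 3 to 5 give response and progression criteria but no alternative PFS definition. Section 10.2 makes the analysis of all endpoints descriptive.

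**The concern.** PFS should describe how long patients remain both alive and free of progression. A patient who dies of toxicity, infection or heart disease before progressing has stopped being progression-free and alive, and can no longer progress. That death is a competing event. Censoring it assumes that the patient's later risk of progression would have matched that of patients still under observation. What is then estimated is a cause-specific time to progression or CMML death, in a hypothetical setting where other deaths do not occur.

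The result also depends on who decides the cause of death, and how. The trial is open-label and Section 2.1 gives a median presentation age of 75. Section 11.1.4 lists neutropenic sepsis and grade 4 haematological toxicity as expected serious events related to CMML, while Appendix 11 advises careful monitoring for haematological toxicity of the drug. A fatal neutropenic sepsis could therefore be attributed to CMML (a PFS event), to tefinostat (censored) or to infection (censored). No adjudication is described.

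At stake is the credibility of one secondary efficacy estimate. Sections 4.3 and 10.5 set the 18-month minimum follow-up in order to assess overall survival and PFS.

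**Working it through.** The protocol states no PFS estimate, event count or power, so there is no figure to reproduce. The check covers direction first, then size under stated assumptions.

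**Direction.** With n patients at risk and d events at a given time, Kaplan-Meier multiplies the curve by (1 − d/n). Recoding a death as censored removes a factor below 1. The patient leaves the later risk sets either way, so later factors do not change. The estimate can only stay equal or rise.

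**Inputs for size**
- Share s of first events (progression or any death) that are non-CMML deaths before progression: not in the protocol; assumed 10%, 20%, 30%.
- Median m with all deaths counted: not in the protocol; assumed 9 months, range 6 to 12.
- Constant cause-specific hazards: assumed.

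**Formulas.** With λ = ln 2 / m:
- all deaths as events: S(t) = exp(−λt) = 0.5^(t/m)
- protocol rule: S(t) = exp(−λ(1 − s)t) = 0.5^(t(1 − s)/m)
- apparent median: m/(1 − s)

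**Median under the protocol rule, m = 9:** 9/0.9 = 10.0 months; 9/0.8 = 11.25 months; 9/0.7 = 12.9 months. The multiplier runs from 1/0.9 = 1.11 to 1/0.7 = 1.43 whatever m is.

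**12-month PFS.** For example, with m = 9 and s = 20%, 0.5^(12/9) = 39.7% and 0.5^(12 × 0.8/9) = 47.7%.

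| m (months) | All deaths as events | s = 10% | s = 20% | s = 30% |
|---|---|---|---|---|
| 6 | 25.0% | 28.7% | 33.0% | 37.9% |
| 9 | 39.7% | 43.5% | 47.7% | 52.4% |
| 12 | 50.0% | 53.6% | 57.4% | 61.6% |

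The smallest gap is 53.6 − 50.0 = 3.6 points and the largest is 37.9 − 25.0 = 12.9 points: about 4 to 13.

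**Worked example at the planned size.** Take 40 patients, k non-CMML deaths before the first progression, 20 progressions by month 12, and no other censoring before then. With all deaths as events, 12-month PFS is (20 − k)/40. Under the protocol rule it is (20 − k)/(40 − k).

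| k | All deaths as events | Protocol rule |
|---|---|---|
| 2 | 18/40 = 45.0% | 18/38 = 47.4% |
| 4 | 16/40 = 40.0% | 16/36 = 44.4% |
| 6 | 14/40 = 35.0% | 14/34 = 41.2% |

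**The case against.** The strongest reply is that nothing decisive rests on PFS. It is one of several secondary outcomes, its analysis is descriptive, and the stage 1 rule and final recommendation in Section 10.1 use only response and toxicity counts. The definition is explicit, and because date and cause of death are collected, an all-cause version can be derived at any time. The size rests on assumed inputs: the phase I study in Section 2.3.3 had no dose-limiting toxicities, so a frequency of toxic death has not been shown. Sampling error is also large. At 40% with 40 patients, the approximate 95% half-width is 1.96 × √(0.4 × 0.6/40) = 15 points. All of this stands and limits the severity. It does not remove the defect: the protocol itself fixes the event and the censoring rule, and imprecision does not excuse a bias of known direction.

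A reader might infer more than the documents support:

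- **That toxic deaths are hidden.** They are not. Overall survival counts every death, the primary safety endpoint counts drug-related deaths in the first two cycles, and treatment-related deaths trigger an IDMC report. A toxic death after cycle 2 falls outside the primary safety endpoint but still counts in overall survival.
- **That a toxic death improves the PFS curve.** This is true only against coding that death as an event. Against the same patient remaining event-free, censoring shrinks the risk set and makes later drops as large or larger.
- **That every non-CMML death is censored.** Only deaths before progression are affected.
- **That sepsis deaths will be censored.** The Section 11.1.4 classification serves safety reporting and does not settle cause of death for PFS. It shows that attribution is ambiguous, and such a death might count as an event.
- **That the estimate cannot be compared with other series.** The protocol plans no external PFS comparison; its stated benchmark is response rate, 10% against 30%. How other series define PFS cannot be checked from this document.

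**Conclusion.** The point holds as a should-fix. Section 10.4.2 gives the name progression-free survival to a disease-specific endpoint. Non-CMML deaths before progression, including those attributed to tefinostat, are competing events that it treats as censoring. As an estimate of time alive without progression, the curve is biased upward whenever such deaths occur, and it varies with unadjudicated cause-of-death attribution.

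The direction is certain and the size is not. The range of about 4 to 13 points at 12 months, and 1.11 to 1.43 on the median, depends on the assumed 10% to 30% share, the assumed 6 to 12 month all-cause median and constant hazards. If no such death occurs, the bias is zero. The go/no-go rule does not use PFS, so a reader who took this as invalidating the trial's decision would be going beyond the protocol.

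**What to change.** In Section 10.4.2, replace the event and censoring sentences so that:
- PFS runs from registration to the first of progression or death from any cause;
- only patients alive and progression-free are censored, at their last disease assessment.

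If a disease-specific measure is wanted, add the cumulative incidence of progression, with death without progression as a competing event, under its own name.

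The cost is two sentences and no new data on deaths, since Section 11.6 already collects date and cause. Reported PFS becomes slightly less favourable. The change should be made before the analysis, because altering the event definition once results are known would be open to challenge.
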